## 6.2.6. Week 16 Clinic Visit (Primary Efficacy Time Point)

#### 6.2.6.1. Pre-dosing

• Review subject eligibility.

**NOTE:** At the Week 16 visit, subjects must have a 30% or greater reduction in WOMAC Pain subscale relative to Baseline in the index joint and a 15% or greater reduction in WOMAC Pain subscale from Baseline at either Week 2, 4 or 8 in order to continue investigational product. As a risk mitigation measure, subjects who do not meet this efficacy response criteria will be discontinued from the Double-blind Treatment period and enter the 24-week Early Termination Follow-up period (refer to Section 6.4). The efficacy response calculation will be performed by the IRT system.

- Adverse event review.
- WOMAC (all subscales).
- Patient's Global Assessment of Osteoarthritis.
- WPAI:OA.
- EQ-5D-5L.
- TSQM (v.II).
- mPRTI.
- Lower Extremity Activity Scale (LEAS).
- Vital signs after sitting for at least 5 minutes, (blood pressure, and heart rate).
- Orthostatic blood pressure (supine/standing) measurement.
- Musculoskeletal physical examination.
- Neurologic exam/Neuropathy Impairment Score (referral for neurological consult if required).
- Serum and plasma retention samples.

- Clinical laboratory tests (blood chemistry and hematology).
- Blood sample for PK analysis (refer to Section 7.5).
- Blood sample for anti-tanezumab antibody assessment (refer to Section 7.3.14).
- Blood and urine samples for biomarkers (fasting if possible, urine sample should be from 2nd void of the day or after; refer to Section 7.6).
- Urine pregnancy test for females of childbearing potential (must be negative prior to dosing).
- Sites performing activity level monitoring (actigraphy) will collect activity level monitors from subjects.
- Concomitant medication review/update.
- Subject daily/weekly IRT entry compliance (daily index joint pain score, weekly non-index joint pain assessment and as applicable, daily rescue medication and weekly NSAID use entries).
- Instruct subjects that after the Week 16 visit the index joint pain score, non-index joint pain assessment, rescue medication and NSAID use will all be assessed once weekly using IRT (See Section 7.1).
- Monitor for violations of concomitant NSAID (outside of oral investigational product) use.
- Review daily and weekly (as applicable) joint pain scores.
- Rescue medication (acetaminophen/paracetamol) compliance review/dispense.

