A table showing number and percentage of subjects will summarize the response for each dimension (item) of the EQ-5D-5L at Baseline and Weeks 8, 16, 24, 40, 56 and 64. These summary tables will be shown by treatment group. In addition, for each treatment and each time point assessed, descriptive statistics (mean, standard deviation, median, number of subjects) will characterize the five-item health status profile on the EQ-5D-5L in terms of the health utility score and the EQ-VAS.

Summaries of the change from Baseline to Weeks 16, 24, 56 and 64 in the WPAI:OA impairment scores will be shown by treatment group.

All data from TSQM and mPRTI will be summarized by visit. The domains of the TSQM (satisfaction with effectiveness, side effects and convenience and overall satisfaction) and two items of the mPRTI (patient willingness to use drug again; patient preference of drug versus prior treatment) will be analyzed using the Cochran-Mantel-Haenszel test (stratified by the combination of the three stratification factors) at both Weeks 16 and 56. For any analysis using the Cochran-Mantel-Haenszel test, if there are too few subjects in any stratification combination group then an unstratified test will be performed. The HCRU data will be reported as outlined in the Statistical Analysis Plan.

All endpoints up to Week 64 will be summarized (where available), and endpoints up to Week 56 will be analyzed. Any efficacy data collected at the Week 64 visit will be excluded from summary and analyses of efficacy with the following exception: Any efficacy data collected at the Week 64 visit for subjects that have discontinued the study early, and the observations are within 10 weeks after the last dose (8 weeks plus a window of 2 weeks) can be included in the efficacy summaries and analyses for the appropriate efficacy window in which the data falls.

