6.4. Covariates

For all models analyzing the continuous primary and secondary efficacy endpoints (except rescue medication) the corresponding Baseline value will be used as a covariate, in addition to Baseline diary average pain. Study site will be fitted as a random effect in the ANCOVA models. The randomization stratification variables of index joint (hip or knee), NSAID cohort (celecoxib, naproxen and diclofenac), and highest Kellgren-Lawrence grade of any Hip/Knee joints (grade 2, 3 or 4) will be included as fixed effects.

A listing of subjects with mis-matches between the stratification variables entered at randomization and the case report form data (including central lab data for Kellgren-Lawrence grade) will be provided. In analysis models, the strata entered at randomization will be used, but for descriptive summarization of the population and identification of subgroups, the strata as indicated on the case report form data will be used.

For the models analyzing the amount and number of days of rescue medication use the model will include terms for Baseline WOMAC Pain, Baseline diary average pain and stratification factors.

The analysis of the incidence of treatment discontinuation due to lack of efficacy will include model terms for baseline WOMAC Pain subscale score, Baseline Diary Average Pain, index joint, Kellgren-Lawrence grade, NSAID group and treatment group.

0900177 (e-s) 1811656 Approved Approved On: 03-10-2019 08:56 (GMT)

For treatment response endpoints relating to WOMAC Pain and PGA, the Baseline WOMAC Pain and PGA values will be used respectively as covariates in the analysis model, in addition to the stratification parameters of index joint, highest Kellgren-Lawrence grade of any hip or knee joint, NSAID group and Baseline diary average pain. For the OMERACT response value, the Baseline WOMAC Pain subscale score will be used to represent the Baseline score covariate, in addition to the covariates named above (Baseline diary average pain, and the three stratification factors).

Additional analyses of the three co-primary endpoints will examine the treatment interactions with Study site and Country. Note, separate analyses will be performed for the individual NSAID groups.

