The change from Baseline in the Lower Extremity Activity Scale to Weeks 4, 8, 16, 24, 56 and 80 and worst post-Baseline score will be analyzed using CMH test and stratified by the combined levels of the three stratification factors (Section 6.4). LOCF will be used for imputation of missing data. The change from Baseline to all weeks (including Week 80) will be summarized showing the number and percentage of subjects with any worsening score (change<0), no change, or improvement (change>0), as well as each category of change, and mean (with standard deviation) and median change.

The CMH test will be stratified by the combinations of the three stratification factors (Section 6.4). For any analysis using the CMH test, if there are too few subjects in any stratification combination group (defined as <15 subjects in any stratification factor) then an unstratified test will be performed.

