The Weeks 16 and 56 responses in the 4 TSQM parameters of satisfaction with effectiveness, side effects and convenience, and overall satisfaction will be summarized. The 11 questions of the TSQM are used to calculate the 4 endpoints of Effectiveness, Side Effects, Convenience and Global Satisfaction, each scored on a 0-100 scale with 100 being the best level of satisfaction.

The four parameters of the TSQM will be analyzed using the ANCOVA model described above for the primary endpoint using covariates of the Baseline diary average pain, Index Joint, Highest KL grade (2, 3 or 4), NSAID cohort and Treatment, with Study Site as a random effect at both Weeks 16 and 56. Summary tables showing number and percentage of subjects by value and treatment group will be shown for the TSQM items 1-11, and the four satisfaction parameters.

This summary and analysis will use observed data only (no imputation for missing data). The calculation of these endpoints is described in [Appendix 1.4](#).

10. Patient Reported Treatment Impact Assessment-Modified (mPRTI) at Weeks 16 and 56.

The mPRTI is collected at Weeks 16 and 56. The two endpoints derived from this questionnaire are described below:

- Patient willingness to use drug again. This comes from the question “In the future, would you be willing to use the same drug that you have received in this study for your osteoarthritis pain?” This is rated on a 5 point Likert scale from 1 (‘Yes, I would definitely want to use the same drug again’) to 5 (‘No, I definitely would not want to use the same drug again’).
- Patient preference of drug versus prior treatment. This comes from the question “Overall, do you prefer the drug that you received in this study to the treatment you received before this clinical trial?” This is rated on a 5 point Likert scale from 1 (‘Yes, I definitely prefer the drug I am receiving now’) to 5 (‘No, I definitely prefer my previous treatment’).

The two parameters of the mPRTI will be analyzed using the CMH test (stratified by the combinations of the three stratification factors) at both Weeks 16 and 56. If there are too few subjects in any stratification combination group (defined as <15 in any strata level) then the analysis will be modified to an unstratified test. Summary tables showing number and percentage of subjects by value and treatment group will be shown for all mPRTI questions.

This summary and analysis will use observed data only (no imputation for missing data).

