09001776e193181b656Approved\Approved On: 08-10-2019 08:56 (GMT)

11. Lower Extremity Activity Scale.

The LEAS is an 18-point scale ranging from 1 ('I am confined to bed all day') to 18 ('daily vigorous physical activity'), and is collected at Baseline and Weeks 4, 8, 16, 24, 56 and 80.

The number and percentage of subjects whose activity score is improved (increased), worsened (decreased) or have no change, and each level of change will be shown by treatment group for each week, using LOCF for any missing data. The mean (with standard deviation) and median change will also be summarized. The change from baseline to each post-Baseline visit (using LOCF for missing data), and for the worst change from Baseline (over all post-Baseline visits) will be summarized, and analyzed using CMH test (stratified by the combinations of the three stratification factors) (note, Week 80 data will be summarized, but not analyzed). If there are too few subjects in any stratification combination group (defined as <15 in any strata level) then the analysis will be modified to an unstratified test.

12. Accelerometry Endpoints.

The five accelerometry endpoints will be collected prior to Baseline (at least 4 days, with 1 being a weekend day) and prior to Weeks 16 and 56 (at least 8 days, with 2 being weekend days). The change from Baseline to Week 16 and 56 will be calculated for these parameters. Summaries and analyses of these endpoints will use observed data for change from Baseline to Weeks 16 and 56, and imputation using LOCF for Week 56.

These parameters will be analyzed using a negative binomial model using covariates of the corresponding Baseline accelerometry score, Baseline diary average pain, Index Joint, Highest KL grade (2, 3 or 4), NSAID cohort and Treatment.

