Incidence of secondary composite endpoint, individual adjudication joint safety endpoints (RPOA-1, RPOA-2, RPOA-1/2, SIF, Primary ON, Pathological fracture), TJR, and TJR and any adjudication outcome	ITT	Exact analyses for risk difference and ratio (percentage)	Treatment group	Observed	Secondary Joint Safety Analyses
Time to joint safety event (Primary Composite, Secondary Composite, Individual Adjudication Events, TJR, TJR and any adjudication outcome)	ITT	Log-Rank (with KM estimates)	Treatment Group	Observed	Secondary Joint Safety Analyses
Incidence of Bland-Altman defined progression of OA for subjects with OA of the Hip (KL2,3) at Weeks 56/ET and 80/ET, and Weeks 56 and 80 (based on window)	ITT	Logistic Regression	BL JSW, Treatment Group	Observed	Radiographic safety endpoint
Incidence of Bland-Altman defined progression of OA for subjects with OA of the Knee (KL2,3) at Weeks 56/ET and 80/ET, and Weeks 56 and 80 (based on window)	ITT	Logistic Regression	BL JSW, Treatment Group	Observed	Radiographic safety endpoint
Change from Baseline in JSW for subjects with OA of the Hip (KL 2, 3) at Weeks 56/ET and 80/ET, and Weeks 56 and 80 (based on window)	ITT	ANCOVA	BL JSW, Treatment Group (Study site as a random effect)	Observed	Radiographic safety endpoint
Change from Baseline in JSW for subjects with OA of the Knee (KL 2, 3) at Weeks 56/ET and 80/ET, and Weeks 56 and 80 (based on window)	ITT	ANCOVA	BL JSW, Treatment Group (Study site as a random effect)	Observed	Radiographic safety endpoint
Change from baseline to Weeks 2, 4, 8, 16, 24, 32, 40, 48, 56, 64 and 80 in the NIS score, and Change from Baseline to Worst post-Baseline NIS score	ITT	CMH test	Treatment Group [1]	LOCF (Weeks 2, 4, 8, 16, 24, 32, 40, 48, 56, 64, 80), Worst post-baseline score	Safety Analysis
Survey of Autonomic Symptoms (SAS), number of symptoms and total impact score (by visit and change from Baseline)	ITT	Summary	NA	Observed	Safety Analysis

[1] CMH test will be stratified by the levels of the combined stratification parameters (18 levels). If there are <15 subjects in any combined stratification level then the CMH test will be unstratified.

09001776e49378b656\Approved\Approved On: 08-10-2019 08:56 (GMT)

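### One sparse cell out of 18 removes all strata from the CMH tests, with a trigger worded three ways; in the full ITT set the fallback protects nothing and can be deleted

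*SAP*

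**What the plan says.** Randomisation is stratified by index joint, highest KL grade and screening NSAID, giving 18 groups, or 6 in Japan, where every subject takes celecoxib (Protocol 3, Table 5). The CMH tests of PGA, NIS, LEAS and mPRTI use the same combined strata. The instruction to abandon them appears in several places:

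- SAP 8.2.5, footnote [1]: "If there are <15 subjects in any combined stratification level then the CMH test will be unstratified".
- SAP 8.1.2, for every CMH analysis: "if there are too few subjects in any stratification combination group (defined as <15 subjects in any stratification factor) then an unstratified test".
- SAP 8.2.2, item 10 (mPRTI): "If there are too few subjects in any stratification combination group (defined as <15 in any strata level) then the analysis will be modified". Item 11 (LEAS) uses the same bracketed definition: "If there are too few subjects in any stratification combination group (defined as <15 in any strata level".
- Protocol 9.2.2, with no number: "if there are too few subjects in any stratification combination group then an unstratified test will be performed".

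The missing-data rules differ by endpoint. PGA, LEAS and NIS carry data forward, although NIS does not carry baseline forward. For mPRTI, SAP 8.2.2 item 10 states: "This summary and analysis will use observed data only (no imputation for missing data".

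**The concern.** One thin cell, most plausibly a hip with KL grade 2 in one NSAID cohort, would strip all three factors from the whole test. The CMH mean-score statistic sums observed minus expected over strata. A small stratum adds little to that sum but does not make it invalid, so a count of 15 guards against no identifiable failure in a trial of this size.

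The trigger is also not one rule. A combined level, a stratification factor and a strata level are different units. Nothing says whether subjects are counted over the two arms compared or all three, or among randomised or analysed subjects. The choice of test therefore depends on an undefined count. At stake are a little power, a predictable method, and comparability of mPRTI results between Weeks 16 and 56.

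**Working it through.** **Strata.** 2 joints × 3 KL grades × 3 NSAIDs = 18, as SAP 8.2.5 states. In Japan 2 × 3 × 1 = 6, so 18 − 6 = 12 levels are empty by design. Read literally, the footnote always fires there.

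**Unit.** Protocol 3 sets a minimum of 660 per NSAID cohort, about 220 per arm. Two arms give about 440, so read per factor an NSAID cohort could never trigger the rule. Read per combined cell, firing depends on hip and KL shares, which the documents do not give.

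**Does it fire?** Multinomial draws of the 18 cells, with equal cohorts and KL 4 at 30% (all assumed):

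- Hip 15%, KL 2 15%. Expected smallest cell on two arms: 2000 × 1/3 × 0.15 × 0.15 = 15.0; chance that some cell is below 15: 85%. On three arms: 3000 × 1/3 × 0.15 × 0.15 = 22.5; chance 11%.
- mPRTI, hip 20%, KL 2 20%, two arms. With 1900 observed the smallest cell is expected to hold 25.3 and the chance is 3%. With 1200 observed these become 16.0 and 76%.

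Over hip 10–20% and KL 2 15–25% the two-arm chance runs from about 0 to 100%.

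**Size of the stratified test.** In simulations of the full trial with sparse cells (hip 10%, KL 2 10%, cohorts 22/22/56, N = 3000; expected smallest cell 3000 × 0.10 × 0.10 × 0.22 = 6.6), type I error was 4.6–5.2% stratified and 3.9–5.2% unstratified. Stratifying kept 99.96% of the information. A check with 5-point scores, N = 2000 and very sparse cells gave 5.4–5.5% stratified.

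**Power for PGA.** The plan states no power for any CMH test. Protocol 9.1 gives SD 0.92, 1000 per arm, and differences of 0.11 (2.5 mg) and 0.21 (5 mg). The share of variance explained by strata, R², is assumed. With arms balanced within strata both tests use the same difference d:

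- SE = 0.92 × √(1 − R²) × √(2/1000).
- Stratified power = Φ(d/SE − 1.96).
- The unstratified test leaves strata variance in its SE, so its effective critical value is c = 1.96/√(1 − R²). Its power is Φ(d/SE − c) and its type I error is 2(1 − Φ(c)).

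For d = 0.11:

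| R² | d/SE | c | Stratified power | Unstratified power | Unstratified type I error |
|---|---|---|---|---|---|
| 0 | 2.67 | 1.96 | 76.2% | 76.2% | 5.0% |
| 0.02 | 2.70 | 1.98 | 77.1% | 76.5% | 4.8% |
| 0.06 | 2.76 | 2.02 | 78.7% | 76.9% | 4.3% |
| 0.10 | 2.82 | 2.07 | 80.5% | 77.4% | 3.9% |
| 0.20 | 2.99 | 2.19 | 84.8% | 78.8% | 2.8% |

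For d = 0.21, d/SE is at least 0.21/0.0411 = 5.1, and power is at least 99.9% under either test at every R² shown.

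**Week 56 mPRTI.** With assumed retention of 45–60% and R² of 0.02–0.06, simulated unstratified error was 4.0–5.5% if dropout by stratum is the same in both arms, 4.9–6.7% if it differs mildly, and 6.5–12.7% if it differs strongly. Stratified error was 4.1–5.9%, averaging 5.0% (Monte Carlo SE 0.4 points). At about 90–93% retention with mild differences, unstratified error was 4.8–5.1%.

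**Small subsets.** Six strata, with the effect set so that the unstratified test has roughly 70–75% power. N counts all three arms and is assumed:

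| N | Information kept | Stratified vs unstratified power, R² 0 | Same, R² 0.10 |
|---|---|---|---|
| 30 | 91% | 65.1% vs 70.1% | 68.4% vs 71.4% |
| 60 | 96% | 71.6% vs 73.6% | 76.1% vs 75.1% |
| 120 | 98% | 74.3% vs 75.2% | 77.5% vs 75.4% |

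**The case against.** The strongest reply is that the fallback is pre-specified, valid when arms are balanced within strata, and errs on the safe side. That stands for PGA and LEAS, and nearly so for NIS. The PGA CMH test is also only a sensitivity analysis to an ANCOVA that already adjusts for all three factors.

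A reader might infer that the rule creates a false-positive problem for mPRTI, because Protocol 6.2.6.1 says "subjects who do not meet this efficacy response criteria will be discontinued from the Double-blind Treatment period". The documents do not support this as a general claim. mPRTI is collected at the Week 16 visit itself and again at Early Termination Visit 1, and the SAP's Week 16 window runs from Day 2 to Day 253 (Appendix 1.1). Week 16 data should therefore be nearly complete. Only Week 56, whose window opens at Day 254, could be exposed. Even there the inflation needs dropout that differs by both arm and stratum, and it arises from analysing observed data only as much as from the threshold of 15.

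A reader might also infer that SAP 6.4 already requires stratification: "In analysis models, the strata entered at randomization will be used". That sentence settles which recorded stratum values to use. It does not require every test to be stratified, and the SAP's log-rank tests and joint-safety Poisson models are not.

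Finally, deletion is not free everywhere. A stratum with subjects in only one arm contributes nothing, which costs power in very small sets. SAP 6.5 plans separate Japan tables without giving their size or content, so small subsets need some provision.

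**Conclusion.** The point holds for the full ITT set. The fallback drops three stratification factors for no gain in error control, and its trigger is defined inconsistently. The loss is small: 0 to 1.8 power points for the 2.5 mg PGA comparison at R² up to 0.06, about 3 at 0.10, and none for 5 mg. An excess over 5% is possible only for Week 56 mPRTI and rests on assumed retention and dropout patterns.

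R², hip and KL shares, retention and Japan numbers are all assumptions, so the documents cannot show whether the rule would fire. The calculations take the mean-score form of the test throughout; the SAP specifies row mean scores only for NIS. A reader might infer that deleting the rule is costless in every analysis. The small-subset results show otherwise: about 5 points lost at N = 30 with uninformative strata, about 1 point lost by N = 120, and a gain there if strata are prognostic. No primary or multiplicity-controlled conclusion depends on this, so the change is desirable rather than essential.

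**What to change.** Before unblinding, for the full ITT set, delete the unstratified fallback in SAP 8.1.2, SAP 8.2.2 items 10 and 11, and SAP 8.2.5 footnote [1], and always stratify the CMH tests by the randomisation strata. All four places must change together, or a new contradiction results. Add one sentence stating that this supersedes the fallback in Protocol 9.2.2; Protocol 9 allows the SAP to modify such plans. The questions of unit and arms counted then disappear for the full set.

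For small subsets, including any CMH tests in Japan tables, name the 6 applicable strata and pre-specify collapsing of sparse cells, for example by merging KL grades within index joint, instead of dropping all strata. State the threshold and which subjects and arms are counted.

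The cost is wording and a simple collapsing rule; no new data are needed. The downside is a few power points in very small subsets if cells are left uncollapsed.

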10. APPENDICES

Appendix 1. DATA DERIVATION DETAILS

Appendix 1.1. Definition and Use of Visit Windows in Reporting

Study visits are planned at Screening, Baseline and then at post-baseline Weeks 2, 4, 8, 16, 24, 32, 40, 48, 56, 64 and 80. If a subject discontinues from the trial then there will be an Early Termination Follow-Up period and for those who refuse, ideally, an Early termination visit. To account for this visit and any early or late scheduled visits (compared to the target study days) we define ‘windows’ to be able to allocate each efficacy observation to a single specific study visit. For the assessments made at each planned study visit (eg, WOMAC subscales, Patient Global Assessment of Osteoarthritis etc.) these visit windows are shown below. When multiple observations occur in a visit window, the observation closest to the protocol specified target day will be used, noting that the latter will be used in the case of a tie.

Visit	Target Study Day	Window
Screening [1]	Variable (up to 37 days prior to baseline visit)	[No lower limit, Day -8]
Baseline	1 (defined as initial day of study drug administration)	[-7,1]
Week 2	15	[2,22]
Week 4	29	[23,43]
Week 8	57	[44,85]
Week 16	113	[86,141]
Week 24	169	[142,197]
Week 32	225	[198, 253]
Week 40	281	[254, 309]
Week 48	337	[310, 365]
Week 56	393	[366, 421]
Week 64	449	[422, 477]

[1] Only efficacy data collected at screening is WOMAC Pain subscale.

One additional window will be created relative to the date of last SC dose for summaries of efficacy data collected beyond the planned treatment period. This window will include data from 16 +/- 4 weeks past the date of the last SC dose. The target day is 113 days after the last SC dose, with a window of [85, 141] days after the last SC dose. If multiple observations occur in this visit window, the observation closest to the specified target day will be used, noting that the latter will be used in the case of a tie.

For the assessments not made at each planned study visit, broader visit windows are shown below. When multiple observations occur in a visit window, the observation closest to the protocol specified target day will be used, noting that the latter will be used in the case of a tie.

LEAS

Visit	Target Study Day	Window
Baseline	1 (defined as initial day of study drug administration)	[-7,1]
Week 4	29	[2,43]
Week 8	57	[44,85]
Week 16	113	[86,141]
Week 24	169	[142,281]
Week 56	393	[282, 477]
Week 80/End of Study	561	[478, no upper limit]

EQ-5D-5L

Visit	Target Study Day	Window
Baseline	1 (defined as initial day of study drug administration)	[-7, 1]
Week 8	57	[2, 85]
Week 16	113	[86, 141]
Week 24	169	[142, 225]
Week 40	281	[226, 337]
Week 56	393	[338, 421]
Week 64	449	[422, no upper limit]

WPAI: OA

Visit	Target Study Day	Window
Baseline	1 (defined as initial day of study drug administration)	[-7,1]
Week 16	113	[2,141]
Week 24	169	[142,281]
Week 56	393	[282, 421]
Week 64	449	[422, no upper limit]

Actigraphy, TSQM, mPRTI

Visit	Target Study Day	Window
Baseline	1 (defined as initial day of study drug administration)	[no lower limit, 1]
Week 16	113	[2,253]
Week 56	393	[254, no upper limit]

0900177ed193781b656Approved\Approved On: 08-10-2019 08:56 (GMT)

HCRU

Visit	Target Study Day	Window
Baseline	1 (defined as initial day of study drug administration)	[no lower limit, 1]
Week 64	449	[2,505]
Week 80	561	[506, no upper limit]

For the average pain in the index joint, the data are collected daily via electronic diary up to the end of Week 16, and thereafter weekly up to Week 80. Data up to Week 64 will be reported as part of the efficacy assessment (summary up to Week 64; analysis up to Week 56).

The Baseline score is the mean of the last 3 non-missing pain scores over study days -7 to -1. If fewer than 3 are available between study days -7 and -1, the baseline will be the mean of the available scores.

The table below describes the visit days for each week (Weeks 1-16). All available on-treatment diary data in each of the weekly intervals will be used to calculate the mean daily pain score for that study week.

09001776e1931781b656\Approved\Approved On: 03-10-2019 08:56 (GMT)

Study Week	Days	Study Week	Days
1	1-7	9	57-63
2	8-14	10	64-70
3	15-21	11	71-77
4	22-28	12	78-84
5	29-35	13	85-91
6	36-42	14	92-98
7	43-49	15	99-105
8	50-56	16	106-112

However, if a subject receives the Week 16 injection dose prior to Day 113, the Week 16 score will be calculated using the mean of the available scores from the 7 calendar days immediately prior to the Week 16 injection dose date. Any scores used in this calculation of Week 16 will not also be used in an earlier week calculation, eg, if the Week 16 dose occurs on Day 109, the available scores from Days 102-108 will be used to calculate the average score for Week 16, and the available scores from Days 99-101 will be used to calculate the average score for Week 15.

After the Week 16 visit, pain scores are captured only once a week in the diary. These are grouped in 4-week intervals using visit windows as shown below. If a subject comes in late for a Week 16 visit (or weekly diary is not activated at the visit), and so has daily diary data collected past Day 112, these data will be averaged with any data obtained weekly for any given interval. All available on- or off-treatment data will be used for these windows after the planned treatment period, ie, after Week 56.

Summary Week	Includes Weeks	Days
20	17 - 20	113-140
24	21 - 24	141-168
28	25 - 28	169-196
32	29 - 32	197-224
36	33 - 36	225-252
40	37 - 40	253-280
44	41 - 44	281-308
48	45 - 48	309-336
52	49 - 52	337-364
56	53 - 56	365-392
60	57 - 60	393-420
64	61 - 64	421-448

One additional window will be created relative to the date of last SC dose for summaries of diary pain scores collected beyond the planned treatment period. This window will be identified as 16 Weeks Post Last Dose, and will include the average of all data from 13 to 16

0900177ea1931781b656ApprovedApproved On: 03-10-2019 08:56 (GMT)

weeks (85 to 112 days) past the date of the last SC dose. All available on- or off-treatment data will be used for this window after the planned treatment period.

